4.3.2. Key Secondary Efficacy Analyses

Statistical testing will be performed on the key secondary efficacy endpoints according to the

following hierarchical order. Where applicable, the secondary endpoint will be compared against the null hypothesis for each of the 100 imputed datasets. The outcomes from the 100 imputed datasets will be combined using Rubin's Rule to provide a p-value and corresponding confidence interval as appropriate.

Body Weight Percent Change from Baseline in Patients ≥ 12 Years of Age:

Mean percent change from baseline in body weight for patients in the FAS population will be analyzed after ~52 weeks of treatment. Analyses will be based on a one-sample t-test for each of the 100 imputed datasets and assuming mean percent change from baseline in bodyweight of zero. The outcomes from the 100 imputed datasets will be combined using Rubin's Rule to provide a p-value and corresponding confidence intervals. This will be evaluated at a 1-sided, 0.025 significance level.

Sensitivity analysis based on the DUS population may be provided as needed.

Descriptive statistics for the change and percent change from baseline in body weight (kg) may be presented in the FAS population by active treatment visit.

Daily Hunger Score Percent Change from Baseline in Patients ≥ 12 Years of Age:

Mean percent change from baseline in the weekly average of the daily hunger scores for patients in FAS population will be analyzed after ~52 weeks of treatment. Analyses will be based on a one-sample t-test for each of the 100 imputed datasets with assumed mean percent change from baseline in weekly average of daily hunger scores of zero. The outcomes from the 100 imputed datasets will be combined using Rubin's Rule to provide a p-value and corresponding confidence intervals. This will be evaluated at a 1-sided, 0.025 significance level.

Prior to analysis, daily hunger scores for each of the 3 hunger assessments will be averaged separately by week. For a week of hunger scores to be considered evaluable, scores need to be recorded and available for analysis on at least 1 of 7 days to provide sufficient data to determine mean values.

Rhythm believes that the 1 out of 7 days approach will largely prevent missing data and best utilize the data points available. Unless specified otherwise, this will be applicable for all hunger score related analysis.

Sensitivity analysis based on the DUS population may be provided as needed.

Descriptive statistics for the change and percent change from baseline in weekly average of daily hunger scores may be presented based on FAS population by active treatment visit.

Daily Hunger Score Reduction (Threshold of 25%) in Patients ≥ 12 Years of Age:

The proportion of patients in the FAS population who achieve a \geq 25% improvement from baseline in the weekly average of the daily hunger score after ~52 weeks of treatment will be analyzed similarly to the primary efficacy endpoint. Prior to analysis, daily hunger scores for each of the 3 hunger assessments will be averaged separately by week, as outlined above.

[figure not shown]
Descriptive statistics for the change and percent change from baseline in weekly average of daily hunger scores will be presented based on FAS population for analysis visits. Due to the

34

suitability of using the hunger score tool in younger patients, this will be conducted in patients >=12 years of age at baseline.

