3.8. Subgroups

3.8.1. Subgroup Analysis by Disease Type

Subgroup analysis by disease type (e.g., BBS and AS; clinically defined or genetically defined) on primary efficacy and key secondary efficacy endpoints will be summarized separately. Analysis on the secondary endpoints, i.e., mean percent change of weight and hunger score at ~14 week from baseline, will be conducted for each disease type. A 1-sided p-value and corresponding 95% 2-sided confidence interval will be provided. Please note that the study is not powered for individual subgroups, but powered based on the overall number of the pooled patients across disease types. Thus, the p-values for the subgroup analyses are exploratory and should be interpreted with caution and clinical judgement.

Please note that patients who enter the study based solely on clinical criteria (even if later they are confirmed by genetic testing) will define the "clinically-defined" subgroup. Therefore, appropriate efficacy analysis by disease type subgroups will be performed based on clinically defined subgroup criteria.

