By nature of the study design (as introduced above in Section 1.2), a small percentage of patients who are randomized into the placebo arm may have less than ~52 weeks of setmelanotide treatment by the timing of the primary analysis (when the last patient enrolled has completed Period 2). Hence, the primary analysis will include a multiple imputation (MI) model (SAS PROC MI) that will be used to impute the measurements for patients with less than ~52 weeks of setmelanotide treatment to a timepoint that approximates 52 weeks of setmelanotide treatment. The final multiple imputed datasets will be analyzed using Rubin's rule (with SAS PROC MIANALYZE).

Due to the relatively small number of observation (i.e., number of patients) and large number of the visits (~15 protocol specified visits), there may not be enough observations to fit regression models in the multiple imputation. Therefore, protocol specified visits will be combined as appropriate, and the averaged values (across the combined visits) per the new derived Visit Categories (VC) will be used in the regression in the multiple imputation (SAS PROC MI). The multiple imputation model will contain the following new visit categories (VC) derived as follows:

- VC1=Average (V1, V2)
- VC2=Average of Scheduled Visits between VC1 and VC3
- VC3=Visit Occurring Closest to Day 98/14 Weeks within analysis window
- VC4=Average of Scheduled Visits between VC3 and VC5
- VC5=Visit Occurring Closest to Day 365/52 Weeks within analysis window
- VC6=Average of Scheduled Visits between VC5 and VC7

27

• VC7=Visit Occurring Closest to Day 462/66 Weeks within analysis window

Note, Early Termination visits will be treated as scheduled visits and may slot into any VC as fits criteria. Further, imputation of weight for 52 week analysis will focus on VC5 (for subjects initiated on active treatment) and VC7 (for subjects initiated on placebo) as these VCs are identified similarly, if not exactly, as the true timepoint would be identified, if it were not missing.

The above planned combination of the visits may be adjusted if the model cannot be fitted due to small sample size. Details will be defined in the ADRG.

Once VCs are identified, they will be time aligned by treatment arm before multiple imputation occurs.

That is, subjects initially randomized into the active treatment arm will have:

- VC1
- VC2
- VC3
- VC4
- VC5 (52 Weeks on Active Treatment)

While subjects initially randomized into the placebo arm will have:

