
- VC3
- VC4
- VC5
- VC6
- VC7 (52 Weeks on Active Treatment)

Monotone regression will then be used to impute the missing values, assuming proper missingness structure. The monotone regression method will impute 100 datasets. A seed of 2187 has been randomly generated and will be used.

Fully conditional specification (FCS) regression may be used in the case that monotone regression is deemed not appropriate.

Daily hunger scores will have weekly average hunger score calculated and these weekly averages mapped to Visit Categories with the same algorithm as above.

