4.3.3. Other Secondary Efficacy Analyses of the 14-week, placebo-controlled period

These analyses will be performed on patients in the PCS population, (i.e., on data from the ~14-week, placebo-controlled, randomized, double-blinded period, or Period 1). Where applicable, the secondary endpoint will be compared against the null hypothesis for each of the 100 imputed datasets. The outcomes from the 100 imputed datasets will be combined using Rubin's Rule to provide a p-value and corresponding confidence interval as appropriate.

Body Weight Percent Change from Baseline at 14 Weeks:

The analysis on this secondary endpoint will be a between-group comparison to investigate if setmelanotide-treated patients (\geq 12 years old) exhibit a greater decrease in percent change in body weight from baseline at \sim 14 weeks of therapy, as compared to placebo-treated patients.

This analysis will be based on a two-sample t-test for each of the 100 imputed datasets. The outcomes from the 100 imputed datasets will be combined using Rubin's Rule to provide a p-value and corresponding confidence intervals. This will be evaluated at a 1-sided, 0.025 significance level.

Sensitivity analyses based on PP at EOP1 and CS may be provided.

Descriptive statistics for the change and percent change from baseline in body weight (kg) may be presented for the PCS population by visit by randomized treatment.

Daily Hunger Score Percent Change from Baseline at 14 Weeks

The analysis on this secondary endpoint will be a between group comparison to investigate if setmelanotide-treated patients exhibit a greater improvement from baseline at ~14 weeks of therapy in weekly average of daily hunger scores, as compared to placebo-treated patients. This analysis will be based on a two-sample t-test for each of the 100 imputed datasets. The outcomes from the 100 imputed datasets will be combined using Rubin's Rule to provide a p-value and corresponding confidence intervals. This will be evaluated at a 1 sided, 0.025 significance level.

Prior to analysis, daily hunger scores for each of the 3 hunger assessments will be averaged separately by week, as outlined above. Sensitivity analyses based on PP at EOP1 and CS may be provided.

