[figure not shown]
In order to look at the impact of missing hunger data, a sensitivity analysis may be done to examine if there are any differences in conclusions drawn by data availability; analysis for daily hunger scores will be repeated for patients with at least 3 of 7 days of data present. No imputations will be made for missing data.

[figure not shown]
Treatment Failure Analysis:

In order to look at the impact of missing data on the comparisons between setmelanotide-treated patients and placebo patients after ~14 weeks of treatment, a sensitivity failure analysis may be done. For the non-key, secondary endpoints, patients who have missing 14 week data will be considered treatment failures. Similar to the secondary analyses, this sensitivity analysis will be based on a two-sample t-test for each of the 100 imputed datasets. The outcomes from the 100 imputed datasets will be combined using Rubin's Rule to provide a p-value and corresponding confidence intervals.

Statistical Analysis Plan, Protocol RM-493-023 29 October 2020, Version 3.0

Table 3 Summary of Core Analysis Elements

Endpoints	Analysis Set (1) Primary (Sensitivity)	Main Patient Group	Baseline ⁽²⁾	Subgroup Analysis
Primary				
Proportion of patients who achieve a \geq 10% reduction from baseline in body weight after ~52 weeks of treatment	FAS (SH, AG, PP at EOP2)	≥12 years old	ATB	BBS, AS, <12 yo, <17 yo
Key Secondary (after ~52 weeks of treatment)				
Mean percent change from baseline in body weight	FAS (DUS)	≥12 years old	ATB	BBS, AS, <12 yo, <17 yo
Mean percent change from baseline in the weekly average of the daily hunger score	FAS (FAS: 3/7 daily	≥12 years old	ATB	BBS, AS, <12 yo
	responses, DUS)			
Proportion of patients who achieve a $\geq 25\%$ improvement in the weekly average of the daily hunger score	FAS (FAS: 3/7 daily responses)	≥12 years old	ATB	BBS, AS
Secondary (at the Week 14 visit)				
Mean percent change from baseline in body weight after treatment with setmelanotide as compared with placebo	PCS (PP at EOP1, CS)	≥12 years old	PCPB	BBS, AS, <12 yo, <17 yo
Mean percent change from baseline in the weekly average of the daily hunger score after treatment with setmelanotide as compared with placebo	PCS (PP at EOP1, CS, PCS: 3/7 daily responses)	>12 years old	PCPB	BBS, AS, <12 yo

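### The SAP pools small-sample t-tests over 100 imputed datasets by Rubin's rule without complete-data degrees of freedom; under the standard rule they become z-tests, a small error in the main analyses and a larger one in the six AS patients when data are complete

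*SAP*

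**What the plan says.** SAP 4.3.2 analyses percent change in body weight and in hunger score at about 52 weeks: "Analyses will be based on a one-sample t-test for each of the 100 imputed datasets". On pooling, the same section says: "The outcomes from the 100 imputed datasets will be combined using Rubin's Rule to provide a p-value and corresponding confidence intervals". SAP 4.3.3 does the same against placebo at Week 14: "This analysis will be based on a two-sample t-test for each of the 100 imputed datasets". The number of imputations is fixed in SAP 3.10.1 ("The monotone regression method will impute 100 datasets"), as are the pooling rule and the software: "The final multiple imputed datasets will be analyzed using Rubin's rule (with SAS PROC MIANALYZE"). The criterion is also fixed: "This will be evaluated at a 1-sided, 0.025 significance level".

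SAP 3.8.1 extends the inference to BBS and AS separately: "A 1-sided p-value and corresponding 95% 2-sided confidence interval will be provided". It labels those p-values exploratory. SAP 4.3.4 adds an optional Week 14 analysis that counts patients with missing data as failures, and again "this sensitivity analysis will be based on a two-sample t-test for each of the 100 imputed datasets".

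Nowhere does the supplied text name the reference distribution for the pooled statistic, its degrees of freedom, or a complete-data df setting.

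**The concern.** A t-test in one dataset allows for the SD being estimated from few patients, through n-1 or n1+n2-2 degrees of freedom. Rubin's standard pooling does not carry this forward. Its df reflect only the number of imputations and the fraction of missing information. With 100 imputations and little missing information they are very large, so the small-sample allowance disappears at the pooling step.

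The SAP's own rules push in that direction. Only a small percentage of patients are expected to lack 52-week data for administrative reasons. Under SAP 3.10.2 other missing 52-week values are replaced by baseline, so those patients add no between-imputation variance. If Week 14 failures are given a fixed value, the 100 datasets are identical and the df infinite.

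At stake are the stated 0.025 level and 95% coverage of the key secondary and Week 14 percent-change analyses, and the disease-specific interval for AS, one of the two indications sought.

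**Working it through.** The documents give no operating characteristics for these t-tests, so there is no figure of the plan to reproduce. Their power figures concern the binomial primary endpoint.

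**Inputs from the SAP.** m = 100 imputations (3.10.1); 1-sided 0.025 (4.3.2, 4.3.3); pivotal cohort 38 patients, 32 BBS and 6 AS, all ages (1.1.1); 1:1 randomisation stratified by age group and disease (1.3.2).

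**Assumptions.** 28 to 38 patients aged 12 or over; 14 vs 14 to 19 vs 19 at Week 14; AS split 3 vs 3; fraction of missing information λ from 0.02 to 0.5. No SD or effect size is needed, because size does not depend on scale.

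**Step 1: standard Rubin df.** With r the relative increase in variance due to missing data, df = (m-1)(1+1/r)². Since λ = r/(1+r), this equals 99/λ².

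- λ = 0.02: 99/0.0004 = 247,500
- λ = 0.05: 99/0.0025 = 39,600
- λ = 0.10: 99/0.01 = 9,900
- λ = 0.50: 99/0.25 = 396

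The 97.5% point runs from 1.960 to 1.966, which is a z-test in practice. With λ = 0 the df are infinite.

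**Step 2: size and coverage with nothing imputed.** The true 1-sided size of a 1.96 cut-off is P(t with ν df > 1.96). Coverage is 1 minus twice that. Relative width is 1.96 divided by the correct t value.

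| Analysis | ν | Correct multiplier | Size | Coverage | Relative CI width |
|---|---|---|---|---|---|
| One-sample, n=38 | 37 | 2.026 | 0.0288 | 94.2% | 0.97 |
| One-sample, n=32 | 31 | 2.040 | 0.0295 | 94.1% | 0.96 |
| One-sample, n=28 | 27 | 2.052 | 0.0302 | 94.0% | 0.96 |
| Week 14, 19 vs 19 | 36 | 2.028 | 0.0289 | 94.2% | 0.97 |
| Week 14, 14 vs 14 | 26 | 2.056 | 0.0304 | 93.9% | 0.95 |
| AS one-sample, n=6 | 5 | 2.571 | 0.0536 | 89.3% | 0.76 |
| AS Week 14, 3 vs 3 | 4 | 2.776 | 0.0608 | 87.8% | 0.71 |

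**Step 3: Barnard-Rubin df.** With complete-data df ν, the observed-data df are [(ν+1)/(ν+3)]·ν·(1-λ), and the pooled df are 1/(1/standard df + 1/observed-data df). At λ = 0.05:

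- n=38: (38/40)×37×0.95 = 33.4
- n=28: (28/30)×27×0.95 = 23.9
- n=6: (6/8)×5×0.95 = 3.6

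All three are unchanged to one decimal after combining with 39,600.

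**Step 4: simulation with imputed values.** One-sample test, normal-regression imputation, m = 100, 20,000 replicates, assumed correlation 0.7 with an earlier visit. Where nothing is imputed, the small-sample df are n-1.

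| n | Imputed | Size, standard df | Size, small-sample df | Coverage, standard df | Coverage, small-sample df |
|---|---|---|---|---|---|
| 32 | 2 | 0.0289 | 0.0243 | 94.4% | 95.3% |
| 32 | 4 | 0.0293 | 0.0236 | 94.1% | 95.2% |
| 28 | 2 | 0.0298 | 0.0244 | 94.2% | 95.3% |
| 28 | 4 | 0.0286 | 0.0237 | 94.3% | 95.4% |
| 6 | 0 | 0.0530 | 0.0251 | 89.6% | 95.0% |
| 6 | 1 | 0.0341 | 0.0068 | 93.4% | 98.6% |

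Repeat simulations of one in six imputed gave 0.034 to 0.037 with standard df and 0.007 to 0.009 with Barnard-Rubin df.

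**The case against.** The strongest objection is that this argues from silence. A reader might infer that the SAP prescribes a z-test. It does not: it names t-tests, Rubin's rule and a procedure, and leaves some programming detail to other documents. The z-test follows only if no complete-data df are supplied. That stands, and it makes the point conditional. But the named rule run without that input misses the stated level, so the choice should be written down before the data are seen.

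Second, the main-set error is minor, and trial success rests on the binomial primary endpoint, which these t-tests do not touch. Both are true. A reading that the main percent-change results would be seriously misleading is not supported.

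Third, the large AS figures assume complete data. SAP 4.3.2 and 4.3.3 apply the imputed-dataset procedure where applicable, so an ordinary t-test is within the text when nothing is imputed. With one of six imputed the inflation is much smaller, and with two of six a simulation gave 0.019 under standard df, already below 0.025. The AS p-values are exploratory. For the 52-week endpoints SAP 3.8.1 speaks of summarising by disease, so the one-sample AS test is a reading of the text rather than clearly planned. These limits stand, but a 95% interval covering 88 to 89% is wrong even in an exploratory analysis.

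Fourth, one might extend the concern to children. The documents give no paediatric count, those analyses are optional and may add supplemental-cohort patients, and hunger under 12 is generally descriptive. No paediatric figure can be supported.

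**Conclusion.** The concern holds conditionally. The supplied text gives no complete-data df, and under the standard Rubin df the pooled t-tests are z-tests at any plausible amount of missing data. In the main percent-change analyses the consequence is small and consistent: size about 0.029 to 0.030, intervals 3 to 5% too narrow. This rests on the assumed range of 28 to 38 patients and hardly changes with two to four values imputed. In AS it is material only when data are complete or nearly so, at about 0.054 (one-sample) or 0.061 (3 vs 3). Six is the whole AS cohort; the number aged 12 or over and the actual split by arm are not stated. The change is worth making because it is nearly free and closes an open choice, not because the main conclusions are in doubt.

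**What to change.** In SAP 3.10.1, 4.3.2, 4.3.3 and 3.8.1, state that pooled t-tests use Barnard-Rubin small-sample df, set in PROC MIANALYZE by EDF = n-1 for one-sample and n1+n2-2 for two-sample analyses. Add that where an analysis set has no between-imputation variance (nothing imputed, or every missing value set to a fixed failure value) the ordinary t-test is reported. The second sentence is needed because Barnard-Rubin df do not return exactly to n-1 when λ = 0: for n=6 they give (6/8)×5 = 3.75 instead of 5.

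The cost is a few words and one program option, with no change to data collection or estimand. Intervals widen slightly in the main set. In AS the rule is conservative if any of the six values is imputed (simulated size about 0.007 to 0.009 with one imputed). The SAP should acknowledge this, so that a wide AS interval is not read as evidence of no effect.
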